**Pregnancy and Breast Feeding:**

Since the acceptable levels of radioactivity are lower for pregnant individuals, women will be excluded from participating in this study if they are currently pregnant or might become pregnant during the study. They will be tested for pregnancy as part of the routine laboratory tests. If the test is positive, they will not be included in the study. Before starting the study, we will ask women to avoid becoming pregnant and what precautions they plan to take. We ask women to tell us immediately if they change their minds about becoming pregnant. If the woman is currently breast-feeding, she will be excluded from the study. Women will be given one pregnancy test during the initial physical evaluation, and in addition on day of the PET scans, prior to radiotracer injection.

At the end of the PET scan day, subjects will be assessed (physical and vital signs) by the study physician. Subjects will be discharged when vital signs are within normal limits and when behavioral changes (if any) are found to be not clinically significant by the MD attending to the subject at the PET Center. If subjects experience any adverse events, they will be treated until they become asymptomatic, prior to discharge. In the proposed study and in our ongoing studies, psychiatric patients who are administered a challenge drug may be admitted to an inpatient unit if psychiatric symptoms worsen or become dangerous on the PET scan day. If required the patients will be assessed by [name] in the neurology clinic and may be sent to emergency department, Yale New Haven Hospital, for admission if necessary. All subjects are followed for 1 week (in person the following day and by phone thereafter) following LPS administration or until potential symptoms (self-report and by assessment) resolve.

**Background and potential side effects of LPS administration:**

LPS administration in human subjects is a generally safe experimental procedure that has been used in at least 2,200 subjects (116). Intravenous LPS administration at doses from 2 to 4 ng/kg causes flu-like symptoms such as fever, chills, rigors, malaise, and increased heart rate (117-119). These effects peak at around 90 minutes, and completely disappear within 6-8 hours or less. Of the 2,200 subjects who have received LPS, only four severe adverse events have been reported, all involving bradycardia or sinus arrest (5). This occurred in subjects who either had a history of vasovagal syncope and/or who participated in a protocol in which they were not adequately hydrated. In large cohorts

09/29/12 Version 13

of subjects who received adequate hydration, no such effects occurred (116). We have administered LPS (0.8-1.0 ng/kg) to >30 subjects, including both healthy controls and individuals with psychiatric disorders, at Yale with no unexpected or serious adverse effects. A small study (119) detected gender differences in peripheral cytokine levels after LPS administration, with females having a more pronounced response than males; 50% of our sample will be women so we will be able to explore sex differences. We have not noted particular behavioral differences (e.g., sickness behavior) between men and women receiving LPS to date. A review of the literature published in 2007 (120) describes all the studies wherein LPS was given to human subjects. All articles were reviewed for any potential adverse effects, morbidity or mortality; however, no long-term morbidity or mortality was reported in these more than 1000 healthy volunteers. At a 5 ng/kg dose of EC-5, subjects experienced nausea, vomiting and fever. Consequently, doses of  $\leq$  4 ng/kg have been subsequently used. We are giving 1/10 of that dose. LPS given at 2 ng/mg is not associated with known longterm sequelae or serious adverse events in healthy populations. Subjects (up to 4 total) who did have side effects at doses as low as 2 ng/kg were found to have underlying medical issues. When side effects have occurred, they are remarkably similar. Typically, within 50-90 min following LPS, subjects describe flu-like symptoms such as fatigue, malaise, arthralgias, myalgias, headache, nausea, and often chills that resolve within 3-4 h. Fever, however, is the hallmark of LPS infusion. After a latent period up to 120 min, there is a monophasic increase in fever which peaks at 1-2°C above baseline. The fever may last up to 3-4 h (depending on dose) and resolves without residual effect.

This critical review of all the cases of LPS administration in human subjects concludes as follows, “for well over a century, endotoxin has been intentionally administered to humans for therapeutic purposes, for the evaluation of anti-inflammatory reagents as well as to address basic scientific questions of endotoxin biology. Much has been learned from the use of this model, and it has proved to be remarkably safe. Well over 1,000 subjects have been studied, yet we were able to find documentation of only five serious adverse events, and these were in subjects who were later shown to have vagal hypersensitivity,” (120). Thus, all the available data support that LPS administration in healthy human subjects is safe.

Although there are no studies applying the lipopolysaccharide to Alzheimer’s disease population, endotoxin has been used in the elderly population with age distributions that approximate our cohort. In one study eight healthy young volunteers (median age 24 yr) and nine healthy elderly volunteers (median age 66 years) were compared for their blood pressure, heart rate, core temperature and hourly plasma catecholamine concentration after the administration of 2ng/kg of endotoxin. At baseline the elderly had a higher mean arterial pressure (MAP) of about 10 mm Hg, after the administration of the endotoxin there was a reduction of about 20 mm Hg in the MAP. In almost all cases the maximal response occurred 4-7 hours after the administration of the endotoxin and was associated with fever. In no cases there were hemodynamically critical changes to the blood pressure (128). The same cohort also showed the presence of overactive initial response and prolonged elevation of the inflammatory markers compared to people in their third decade of life (129). The difference between our experimental design and theirs is: 1- we use 1/5 the dose they used as a bolus. 2- We will have a low threshold for using antipyretics. The changes to MAP seem to have most closely followed the temperatures.

Lipopolysaccharide, or Clinical Center Reference Endotoxin (CCRE) will be provided by the NIH Clinical Center and will be stored and prepared by the YNHH IDS pharmacy. CCRE is an investigational drug, [name] has obtained an Investigational New Drug (IND) for its use in humans from the Food and Drug Administration (FDA). CCRE vials will be stored at 2-8°C in a refrigerator in the locked YNHH IDS pharmacy. Preparation of CCRE will be performed by the YNHH IDS research pharmacist. As recommended by NIH, the pharmacist will dissolve the lyophilized CCRE in Sterile Water for Injection USP under a laminar flow hood on the evening before each endotoxin administration. The dissolved CCRE will be stored at 4°C until the following morning. Dissolved CCRE is stable for at least 24 hours at this temperature.

**Fatigue associated with cognitive testing and the discomfort during the PET scanning:**

The entire duration of cognitive testing will be approximately 3 hours, raising the potential risk of fatigue. Fatigue will be addressed by providing appropriate breaks as needed. Also even though the PET and MRI studies are considered safe procedures and do not cause the subject any pain, they are somewhat uncomfortable as the subject must be motionless during the scans.

**Minimizing Risks: Describe the manner in which the above-mentioned risks will be minimized.**

**To minimize risks associated with endotoxin**

- Using 1/10 of the maximum safe dose
- Medically evaluating subjects and including only those with no history of cardiovascular disease, liver failure, atopy, morbid obesity (BMI>35), underweight (BMI<19), vasovagal syncope, acute or chronic inflammatory conditions.
- Adequately hydrating with saline,
- NPO to reduce the risk of vomiting.
- Close monitoring of blood pressure, heart rhythm, and subjective symptoms, and by the continuous presence of two trained medical professionals.

**To Minimize the risk of liver damage**

- We will recruit only non-obese patients with laboratory results with normal LFTs, bilirubin, and PT ranges.
- We will exclude any subject with clinical or laboratory signs of liver damage. Those who are vulnerable to liver damage as a result of the endotoxin exposure will not be studied, making this group very similar to the groups of HC who had tolerated the endotoxin in the past, without problems.
- We will measure LFTs, bilirubin and PT after endotoxin administration to ensure these values do not go up significantly.”

**To minimize the risk of an exaggerated systemic inflammatory response in the Elderly-** We are using a lower dose.

**To minimize risks associated with blood drawing** Only experienced staff and proper technique will be used to minimize risks associated with use of an arterial catheter. Individuals on anti-coagulation and anti-platelet therapy are excluded from the study.

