#### *Imaging visit to PET center:*

On the day of the scan there are two steps performed:

Step 1:

1. arterial line placement (there is no suitable reference region)
2. 1st scan – 120-min emission

Step2:

3. LPS injection 3 hours prior to 2nd scan, fasting for 8 h prior to this injection
4. 2nd scan – 120-min emission
5. Optional blood draw during the PET center visit If the participant agrees, 10-20mls of blood will be taken at 0,1,3 and 6 hours and banked at [name] in [name] Laboratory. These samples will only be stored in [name] laboratory; they will not be added to one of [name] existing repositories. The samples will be used by only the investigators on this project; they will not be made available to outside researchers.

In certain cases, the length of this day may not be tolerated by the subject on the day so that we divide the day into two where Steps 1 and 2 are administered on separate days.

Note: White coat hypertension is a common phenomenon in the elderly population. During the visit to the PET center, the unfamiliarity of the environment, the placement of the arterial line, and other cannulae can have an additive effect to the white coat phenomenon. Subject's will be asked to bring any prescribed hypertension medication to the scanning day. High blood pressure does not predictably increase the risk during endotoxin administration as the latter often reduces blood pressure. Furthermore, patients with unstable hypertension will be excluded from the protocol. However, in the interest of patient safety and ethical consideration of ignoring a possibly significant clinical finding, [name] will implement the following protocol:

1) If blood pressure is raised (SBP > 180 or DBP > 100) and patient is symptomatic:

- a) If the symptoms raise concerns of end organ damage (chest pain, SOB, focal neurological sign, thunderclap headache, etc) the patient will be referred to the ED via ambulance.
- b) If headache is the only symptom and the headache is more severe or different character than the patients habitual headaches, then the experiment will be stopped. The patient's primary care physician will be contacted or the patient will be referred to urgent care.

2) If blood pressure is raised (SBP > 180 or DBP > 100) and patient is asymptomatic (except for regular headaches):

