- 48 hours after the administration of the endotoxin there will be a phone screening using CAM to check for delirium. If there is ongoing delirium then the subject will be directed to immediately go to the emergency room for evaluations and then a follow-up visit can be scheduled with the study doctor
- One week visit: RAVLT, Trail A/B, digit symbol, CAM, ADCS-ADL, MMSE/MOCA, Stroop. 1- 1.5 hrs.

*Optional additional visit for CSF draw*

In volunteers who agree to do so, one 20mls of CSF Sample 0-7days after LPS will be taken at Hospital research unit (HRU) of Yale new haven hospital and banked at [name] in [name] Laboratory. The samples will only be stored in [name] laboratory; they will not be added to one of [name] existing repositories. The samples will be used by only the investigators on this project; they will not be made available to outside researchers.

*Optional additional visits to assess Cognitive Measures with Cog-state Ipad testing*

We may obtain these measures at baseline during the week before LPS injection and the following one during the week after LPS injection. These patients will be separately consented and we will not exclude anyone if they do not accept to do these tasks.

1. Cogstate Battery (30 minutes) – This computerized test battery will assess memory and cognition. The tasks may include:
  - a. International Shopping List Task – a computerized task to assess verbal learning and memory.
  - b. Groton Maze Learning Task – a computerized task to assess executive function and spatial problem solving.
  - c. Detection Task – a computerized task to assess psychomotor function and speed of processing.
  - d. Identification Task – a computerized task to assess visual attention and vigilance.
  - e. One Card Learning Task – a computerized task to assess visual learning and memory.
  - f. One Back/Two Back Tasks – computerized tasks to assess attention and working memory

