If an individual experiences bothersome symptoms after endotoxin administration and wants to stop the study, flu-like symptoms may be treated with acetaminophen (650 mg every 6 hrs- no NSAIDs will be used because of the risk of antiplatelet effects on the arterial line bleed), and anxiety may be treated with lorazepam (0.5 mg every 2 hrs for a maximum dose of 6 mg every 24 hrs). During screening each subject will be asked about medication allergies, and no medication to which a subject may be allergic will be administered. If a subject request so, the study will be stopped and these medications may be administered. In addition, if any of the following symptoms occurs, if of a severity such that it prevents normal activity, the study in that individual subject will be stopped: Chills, headache, malaise, myalgias, arthralgias, fatigue, nausea and vomiting. If a subject's body temperature exceeds 39.2°C the study will be halted and the subject will receive acetaminophen as described above. If these medications are insufficient to lower body temperature, subjects may be transferred to a higher level of care. Subjects will be discharged at the end of the study day, provided that all of the following have occurred: their blood pressure is within 10% of baseline AND their heart rate is within 20% of baseline AND their mental status is normal AND they do not feel physically or mentally unable to return home. The determination will be made by the PI and/or the study physician.

Monitoring of depressive symptoms Subjects will be rated for depressive symptoms using Geriatric Depression Scale before each endotoxin administration and at several time points afterwards. Subjects will also be rated for fatigue and pain with relevant rating scales.

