\*\*\* When resting heart rate is between 60 - 100 beats per minute. Use clinical judgement when characterizing bradycardia among some healthy subject populations, for example, conditioned athletes.

*For systemic symptoms:*

Systemic (General)	Mild (Grade 1)	Moderate (Grade 2)	Severe (Grade 3)	Potentially Life Threatening (Grade 4)
Nausea/vomiting	No interference with activity or 1 - 2 episodes/24 hours	Some interference with activity or > 2 episodes/24 hours	Prevents daily activity, requires outpatient IV hydration	ER visit or hospitalization for hypotensive shock
Diarrhea	2 - 3 loose stools or < 400 gms/24 hours	4 - 5 stools or 400 - 800 gms/24 hours	6 or more watery stools or > 800gms/24 hours or requires outpatient IV hydration	ER visit or hospitalization
Headache	No interference with activity	Repeated use of non-narcotic pain reliever > 24 hours or some interference with activity	Significant; any use of narcotic pain reliever or prevents daily activity	ER visit or hospitalization
Fatigue	No interference with activity	Some interference with activity	Significant; prevents daily activity	ER visit or hospitalization

Myalgia	No interference with activity	Some interference with activity	Significant; prevents daily activity	ER visit or hospitalization
---------	-------------------------------	---------------------------------	--------------------------------------	-----------------------------

*For laboratory values:*

Serum *	Mild (Grade 1)	Moderate (Grade 2)	Severe (Grade 3)	Potentially Life Threatening (Grade 4)**
Sodium – Hyponatremia mEq/L	132 – 134	130 – 131	125 – 129	< 125
Sodium – Hypernatremia mEq/L	144 – 145	146 – 147	148 – 150	> 150
Potassium – Hyperkalemia mEq/L	5.1 – 5.2	5.3 – 5.4	5.5 – 5.6	> 5.6
Potassium – Hypokalemia mEq/L	3.5 – 3.6	3.3 – 3.4	3.1 – 3.2	< 3.1
Glucose – Hypoglycemia mg/dL	65 – 69	55 – 64	45 – 54	< 45
Glucose – Hyperglycemia				Insulin requirements or hyperosmolar coma
Fasting – mg/dL	100 – 110	111 – 125	>125	
Random – mg/dL	110 – 125	126 – 200	>200	
Blood Urea Nitrogen				Requires dialysis
BUN mg/dL	23-26	27 – 31	> 31	
Creatinine – mg/dL	1.5 – 1.7	1.8 – 2.0	2.1 – 2.5	> 2.5 or requires dialysis
Calcium – hypocalcemia mg/dL	8.0 – 8.4	7.5 – 7.9	7.0 – 7.4	< 7.0
Calcium – hypercalcemia mg/dL	10.5 – 11.0	11.1 – 11.5	11.6 – 12.0	> 12.0
Magnesium – hypomagnesemia mg/dL	1.3 – 1.5	1.1 – 1.2	0.9 – 1.0	< 0.9
Phosphorous – hypophosphatemia mg/dL	2.3 – 2.5	2.0 – 2.2	1.6 – 1.9	< 1.6

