## 8. Stopping criteria of the study in response to Adverse Events:

Any of the following will be sufficient reason for cessation of the experiment. Items i-ix were added with the guidance of FDA:

- i. One Serious Adverse Event (SAE) that is possibly or probably study-related;
- ii. One Grade 3 bradycardia or two Grade 2 bradycardias that are considered to be possibly or probably related to endotoxin administration;
- iii. One episode of sinus pause;

- iv. One Grade 2 or 3 tachyarrhythmia (e.g., atrial, supraventricular, etc.);
- v. One Grade 3 or two Grade 2 systolic hypotension episodes that persist and require interventions, other than passive leg raising;
- vi. Death of an enrolled subject unless unequivocally not attributable to study drug (e.g., traumatic injury);
- vii. Occurrence of a life-threatening allergic/hypersensitivity reaction (anaphylaxis) requiring hemodynamic support with vasoactive medications or mechanical ventilation, the signs/symptoms of which include any of the following: bronchospasm, dyspnea, wheezing, stridor, hypoxemia, urticaria, angioedema, hives, and facial or oropharyngeal edema;
- viii. Grade 4 toxicity in a major organ system (liver, kidney, lungs, heart, etc.) in one subject; OR
- ix. Any Grade 3 toxicity in the same major organ system (liver, kidney, lungs, heart, etc.) in two subjects. Grade 3 abnormalities of multiple laboratory parameters that indicate malfunction of a single organ system (e.g., aspartate aminotransferase, alanine aminotransferase, and bilirubin for liver function; blood urea nitrogen and creatinine for renal function) in a subject will be regarded as a single toxicity for purposes of this stopping criterion.
- x. One grade 3 cognitive adverse effect which persists beyond 1 week or two grade 2 cognitive side effects which persist after a week.

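### Stopping rules viii and ix cover the kidney, but no BUN or creatinine is promised after endotoxin, and the one promised safety panel has no time point

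*Combined protocol and SAP*

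**What the plan says.** The Data and Safety Monitoring Plan, under Stopping criteria, lists ten reasons to cease the experiment and says of the first nine: "Items i-ix were added with the guidance of FDA". Rule viii is "Grade 4 toxicity in a major organ system (liver, kidney, lungs, heart, etc.) in one subject". Rule ix stops the study when two subjects have Grade 3 toxicity in the same organ. In explaining how several abnormal values in one organ count as a single toxicity, it gives as an example "blood urea nitrogen and creatinine for renal function".

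Section 6 of that plan, Plan for Grading Adverse Events, grades both analytes. Creatinine is Grade 3 at 2.1–2.5 mg/dL and Grade 4 at "> 2.5 or requires dialysis". BUN is Grade 3 above 31 mg/dL and Grade 4 when dialysis is required.

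The safety bloods after dosing are described in one place, Section V, To Minimize the risk of liver damage: "We will measure LFTs, bilirubin and PT after endotoxin administration to ensure these values do not go up significantly". Chemistry is otherwise a screening test (Exclusion Criteria, item 9).

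**The concern.** A stopping rule that depends on a graded laboratory value needs the value. Here the rule and the grade limits exist for the kidney, but the sample does not. The liver has a sample, but its timing is open: a draw one hour after LPS and a draw a week later would both satisfy the sentence.

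What is at stake is the protection of subjects, not the MARI comparison. The protocol says there are no earlier low-dose endotoxin studies in the elderly and none in Alzheimer's disease, so the stopping rules carry real weight. It also gives a haemodynamic reason to look at the kidney. In the one study of elderly volunteers that it cites (Expected severity of adverse events, item b), mean arterial pressure fell by about 20 mm Hg, with the trough 6 hours after LPS. The periodic safety review (every 4 months or 4 patients) and the per-subject adverse event review do not close the gap, because neither would have a renal value to look at.

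**Working it through.** The plan states no figure on this point, so there is none to reproduce. The check is to go through every contact after dosing and ask whether it yields the values that rules viii and ix can use.

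**Contacts after dosing**
- Scan day, monitoring (Endotoxin Administration; Lipopolysaccharide Administration): vital signs, EKG and symptoms, followed to 360 minutes. No chemistry.
- Scan day, optional blood (Imaging visit to PET center, step 5): "If the participant agrees, 10-20mls of blood will be taken at 0,1,3 and 6 hours and banked". Voluntary and stored for research; no safety assay is named.
- Discharge (Endotoxin Administration): "their blood pressure is within 10% of baseline AND their heart rate is within 20% of baseline AND their mental status is normal", plus the subject feeling able to go home. The LPS risk section adds a physical assessment. No laboratory result is required.
- Next day (Lipopolysaccharide Administration): an in-person contact for all subjects. No test is named, and Safety Visits does not list the contact.
- 48 hours (Safety Visits): telephone delirium screen.
- One week (Safety Visits): "One week visit: RAVLT, Trail A/B, digit symbol, CAM, ADCS-ADL, MMSE/MOCA, Stroop". No blood.
- Six months: neuropsychological and clinical scales. No blood.
- The next-day blood and urine tests mentioned under Dosimetry studies belong to a cited tracer study, not to this protocol.

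**Match to the rules**
- Renal measures named in rule ix: 2 (BUN, creatinine). With a promised sample after dosing: 0 of 2.
- Liver measures named in rule ix: 3 (AST, ALT, bilirubin). Covered by the promised panel, taking LFTs to include AST and ALT: 3 of 3. With a stated time: 0 of 3.

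**What can and cannot be seen**
- Grade 3 renal, without symptoms: creatinine 2.1–2.5 or BUN above 31 mg/dL. Not seen.
- Grade 4 renal, without symptoms: creatinine above 2.5 mg/dL only, since Grade 4 BUN is defined by dialysis. Not seen.
- Dialysis, or a related serious adverse event: seen without any scheduled sample.

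**Timing of a possible draw.** The second scan starts 3 h after LPS and lasts 120 min, so it ends at 3 + 2 = 5 h. Monitoring runs to 360 min = 6 h. The pressure trough in the elderly volunteers was at 6 h. A draw at the end of the scan day is therefore at or before the trough and could hardly show a creatinine rise caused by it. A next-day draw comes after it.

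**Blood volume.** The cap is 150 mL for the whole study. Genotyping takes 10 mL. If the optional 10–20 mL is taken at each of four times, that is 40–80 mL. This leaves 150 − 10 − 40 = 100 mL down to 150 − 10 − 80 = 60 mL for screening, arterial sampling, the promised panel and anything added. The documents give no arterial sampling volume. A sample of 5–10 mL is assumed here for the panel.

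**The case against.** The best reply is that the risk is small and largely covered already. The dose is 0.4 ng/kg against 2 ng/kg in the elderly study, so one fifth (0.4/2). Subjects get 500 mL of saline beforehand and about 100 mL/hr afterwards. Renal failure is an exclusion, and NSAIDs are restricted. The protocol says that no elderly volunteer in that study had a critical blood pressure change. If a subject is hypotensive after the pre-dose antihypertensive allowance, endotoxin is delayed or cancelled. The severe reactions it reports from the wider endotoxin literature are cardiac or vagal, none renal. Rule v acts on persistent hypotension and rule i on any single related serious event. All of this stands, and it is why the expected rate is low. It does not replace the missing value, because none of these measures reveals a symptomless rise, and reports of serious events in mainly healthy volunteers need not have counted such rises.

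It can also be said that rule ix mentions BUN and creatinine only as examples in a counting instruction. That is right, and a reader should not infer that the rule prescribes them as its sole trigger. But both rules name the kidney and the grading table sets renal limits, so the plan assumes that such values may be available.

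Finally, a site might run a full metabolic panel when asked for LFTs. It might, but the text does not require it.

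**Conclusion.** The gap is real and narrow. As written, symptomless renal toxicity of Grade 3 or 4 defined by a laboratory value would not be detected and could not trip rules viii or ix. The liver part of those rules rests on a promised sample with no time. The gap applies to every dosed subject: 16 are planned, and Section VII allows enrolment of up to 20.

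Three stronger readings are tempting and not supported:
- A reader might infer that the kidney provision is inert. It is not: the dialysis criterion and rule i remain live.
- A reader might want the probability that a stop would be missed. The documents give no renal event rate, so any such figure would reflect only the rate assumed.
- A reader might infer that every row of the laboratory grading table needs a sample after dosing. The table is a general scale adopted from FDA vaccine guidance. It grades what is measured and is not a test schedule.

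The conclusion assumes that the plan is followed as written and that LFTs does not mean a full metabolic panel. It should be corrected because the remedy is cheap and the rules were added with regulatory input. It does not affect the primary analysis.

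**What to change.** In To Minimize the risk of liver damage, add BUN and creatinine to the panel and fix its time at the in-person contact on the day after LPS. Add that contact to Safety Visits, which at present omits it, so that the two sections agree. If the next-day contact will not be held, draw at the end of the scan day and again at the one-week visit, accepting that a rise that appears and clears between the two would be missed.

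Grade the results against the existing table before the next subject is dosed, and include them in the principal investigator's per-subject adverse event review. The screening chemistry provides the comparison value.

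The cost is a sentence or two in each of the two sections and one small sample, or two under the fallback. The site should confirm that total blood stays under 150 mL, since the arterial volume is not stated. The payment schedule in Section X has no line for a next-day contact, so holding it may need one; the one-week visit is already paid. Dosing of the next subject would have to wait for the result.
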